12.3 Randomization and Stratification

Patients will be stratified by baseline dyspnea (0-7 versus 8+ for CDS total score) and assigned with equal probability to either RESPeRATE group or the control group using variable length permuted block randomization. Block sizes will be chosen randomly to ensure that future assignments cannot easily be inferred from previous ones. There will be no interim analyses for this pilot study, and analyses will not be done separately for each stratum.

12.4 Primary Endpoint(s)

The primary objective of this study is to collect data that will allow us to assess the feasibility of conducting a phase III randomized study of device-guided breathing in lung cancer survivors with significant anxiety. These endpoints include: participation, accrual, adherence, and retention.

The participation rate will be calculated as the proportion of eligible patients who agree to participate.

The accrual rate will be calculated as the number of patients accrued to the study divided by the number of months of accrual.

The actual amount of time the participant used the device will be retrieved from each device. Adherence will be calculated as the actual amount of time the device is used divided by the prescribed time. Successful adherence will be defined as use of the device $\geq 75\%$ of the time assigned. We will also estimate the proportion of patients who use the device more than prescribed. (If “low-dose” participants use the device more than prescribed, this may limit our ability to detect a dose effect.)

Retention will be calculated as the number of participants who complete the final assessment divided by number randomized.

Confidence intervals for the binomial proportions will be calculated using methods described by Wilson.⁷⁸ Approximate 95% confidence intervals based on the normal distribution will be calculated for the continuous measures.

The clinical endpoints are anxiety (primary outcome: anxiety subscale of the HADS-Anxiety/Depression Scale), cancer-related worry, dyspnea, and pulmonary function at baseline and 6 and 12 weeks post-randomization. Estimates of treatment efficacy will be obtained using the “intent to treat” approach. Descriptive statistics (means, standard deviations, frequencies,

etc.) will be presented for each outcome measure at baseline and follow-up points stratified by treatment arm. Repeated measures (RM) ANCOVA models (fitted using PROC MIXED in SAS) will estimate the treatment effect for each outcome, test for treatment differences, and obtain adjusted post-treatment estimates of the variability of these outcomes. Estimates of outcome measure variability will be used to determine sample size for the subsequent trial. The primary RM ANCOVA model will include time, treatment arm, and the stratification factors. An unstructured covariance matrix will be used to account for the within-patient correlation over time. In secondary models, additional covariance structures (Toeplitz, Autoregressive, Compound Symmetry) will be assessed and the optimal structure will be chosen based on likelihood ratio tests for nested structures and the BIC statistic for non-nested structures. Least squares means and 95% confidence intervals will be provided for each outcome, stratified by treatment arm, and for the difference between treatment arms. Regression diagnostics and residual plots will be used to find appropriate transformations for variables in the model.

Subsequent RM ANCOVA models will include additional covariates (e.g., age, sex, stage) to correct for chance imbalances in important prognostic variables and account for variability in outcome measures due to covariates. These latter models will inform us of possible stratification factors for the subsequent trial. Limited exploratory analyses will be done to determine if the treatment effect differs for different levels of covariates (e.g., by including treatment by covariate interactions in the model) to see if the subsequent trial should be done in particular subsets of lung cancer survivors. It is likely that some data will be missing. In addition to the mixed models above, we will use multiple imputation pattern-mixture models under various assumptions (e.g., participants in the active arms who drop out would have subsequent patterns similar to participants in the control arm) to assess the sensitivity of our modeling assumptions.

The optimal dose will be defined as the one that results in the greatest improvement in anxiety scores at 12 weeks (based on estimates from the RM ANCOVA model). This dose will be used in the subsequent trial, assuming that it is one of the RESPeRATE intervention groups.

Assuming the 95% confidence interval for the treatment effect includes a clinically meaningful difference, the sample size for the subsequent phase III trial will be determined based on detecting a clinically meaningful difference with a high power using estimates of variability obtained in this study. The estimates of retention and adherence observed in this study will be used to refine that sample size estimate. Subsequent trial feasibility will be assessed based on our ability to recruit the required number of participants. For that, we will use the accrual and participation rates observed in the participating sites. For sites that did not participate in this pilot study, accrual will be estimated by multiplying the estimated number of eligible patients times the participation rate across the participating sites.

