7. CLINICAL EVALUATIONS AND PROCEDURES

7.1 Schedule of Events

Participants will be randomized to one of three groups: RESPeRATE device-guided breathing group (low-dose) (n=25), RESPeRATE device-guided breathing group (high-dose) (n=25), and a usual breathing control group (n=25).

The low-dose group will use the RESPeRATE device for 15 minutes once a day, at least 5 days per week for 12 weeks.

The high-dose group will use the RESPeRATE device for 15-minutes twice a day, at least 5 days per week for 12 weeks.

The usual breathing control group will use an identical control device (with nonrhythmic tones that will not gradually slow down to reduce respiration rate) for 15 minutes once per day, at least 5 days per week over 12 weeks.

After randomization, participants will be introduced to their assigned device and receive instructions and a demonstration on use. Participants will use it at least 5 days per week for the assigned amount of time over 12 weeks. All participants will complete pre- and post-intervention questionnaires, spirometry (FEV1) at baseline and Week 12, weekly telephone contact to provide breathing data for the prior 7 days, brief mid-intervention questionnaires by mail with a stamped return envelope enclosed and/or telephone contact at Week 6, and rate symptom intensity while using the devices (before and after one session per week). Eligible participants will collect salivary cortisol samples for three days following baseline and the Week 12 follow-up. Participants with endocrine disorders (e.g., diabetes and thyroid disorders) or on steroid-based medications (topical steroid medications are permitted) are excluded from the cortisol portion of the study. Participants will have a blood draw at the baseline and 12 week visits, to determine if RNA and/or DNA methylation and/or gene expression variation correlates with anxiety changes. The duration of the study is 12 weeks.

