The NCORP staff member will instruct each participant in use of the RESPeRATE device at baseline. Participants will be told that RESPeRATE analyzes a person's breathing pattern and plays 2 distinct tones that guide the person to inhale and exhale. The RESPeRATE control device looks and sounds identical but is not programmed to gradually slow breathing rate as in the active intervention arm. All participants will be provided with written instructions for the assigned device and will be observed using the device during the visit. To enhance adherence, we will have a NCORP staff member call participants weekly to assess experience with the device, troubleshoot difficulties that may have arisen and obtain breathing data for the prior 7 days. Participants who have not been using the device at the recommended frequency will troubleshoot ways of overcoming barriers to adherence as needed.

Self-reported dyspnea and spirometry (FEV1) include questionnaires and a pulmonary function test (PFT). These measures will be administered in-person at the NCORP site during baseline and post-intervention (Week 12) assessments. A shorter battery will be administered mid-intervention via mailed paper questionnaire with a stamped return envelope enclosed (Week 6). Any serious adverse event grade 4 or 5 related to the intervention will be reported to the WF NCORP RB at the time they become known to the NCORP site. (See Section 10.0)

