- Blood draw—a blood sample of approximately 2 teaspoons will be taken from a vein in the arm/central line for DNA methylation levels and RNA.
- Salivary cortisol collection—saliva samples will be collected by participants at time of awakening, 30 minutes post-awakening, and at bedtime for three consecutive days (9 samples per participant).

7.3 Evaluations during Study Intervention at Weeks 1 - 11

Weeks 1 - 11:

- Weekly Check-in Call/Data Capture from Device via telephone interview. The participant will be contacted by phone to assess his/her experience with the device and troubleshoot difficulties that may have arisen and obtain breathing data for the prior 7 days. The participant will also be asked if (s)he completed the once weekly

VAS for distress, anxiety, and dyspnea (before and after a single use of the device each week). If (s)he has not done so, (s)he will be asked to complete the VAS form before and after their next use of the device. Participants who have not been using the device at the recommended frequency will troubleshoot ways of overcoming barriers to adherence, as needed.

Week 6:

- In addition to phone contact, participants are to complete the following questionnaires (may be done via mail):
- Hospital Anxiety/Depression Scale (HADS)
- Cancer Worry Scale
- Cancer Dyspnea Scale
- PROMIS Fatigue
- Manchester Cough in Lung Cancer Scale
- Activities form
- Weekly Check-in Call/Data Capture from Device Form (via telephone)

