12. STATISTICAL CONSIDERATIONS

12.1 Study Design/Endpoints

Objectives: The objectives of this pilot study are:

- 1) To evaluate the feasibility of conducting a randomized phase III study to test the efficacy of device-guided breathing in post-treatment lung cancer survivors with significant anxiety. Feasibility will be assessed using measures of accrual, participation, adherence, and retention.
- 2) To collect preliminary data on the variability and efficacy of two doses of a device-guided breathing intervention versus a usual breathing control group for reducing anxiety (primary outcome) and for improving self-reported cancer-related worry dyspnea, and respiratory functioning (secondary outcomes) in post-treatment lung cancer survivors.
- 3) To select the optimal dose of the device-guided breathing intervention (15 minutes once/day or twice/day) for a subsequent randomized study. The optimal dose will be defined as the one that results in the greatest improvement in anxiety scores at 12 weeks.

A parallel, randomized pilot study will be conducted to address these objectives. Eligible patients will be stratified initial dyspnea level and randomized with equal probability to high dose device-guided breathing, low-dose device-guided breathing, or a usual breathing control. Study endpoints include anxiety (primary outcome: anxiety subscale of the HADS-Anxiety/Depression Scale), dyspnea, and respiratory function. These constructs will be measured at baseline and 6 and 12 weeks post-randomization. Estimates of treatment efficacy will be obtained using the "intent to treat" approach. That is, all randomized patients will be included in the primary analyses whether or not they were treated according to protocol.

- 4) Supplemental Objective: To determine if changes in anxiety attributed to device-guided breathing are correlated with epigenetic (DNA methylation) and/or gene expression changes.
- 5) Supplemental Objective: To obtain preliminary data on changes in salivary cortisol (diurnal slope, cortisol awakening response, area under the curve) in each intervention group and associations between salivary cortisol and anxiety.

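### Section 12 counts pulmonary function at Week 6, but FEV1 is measured only at baseline and Week 12, and its model does not state the role of baseline FEV1

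*Combined protocol and SAP*

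**What the plan says.** Section 12.1 names anxiety as the primary outcome, adds "dyspnea, and respiratory function" as further endpoints, and continues: "These constructs will be measured at baseline and 6 and 12 weeks post-randomization". Section 12.4 repeats the schedule for the clinical endpoints, including "dyspnea, and pulmonary function at baseline and 6 and 12 weeks post-randomization".

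Section 12.4 then sets out one repeated-measures ANCOVA, fitted in PROC MIXED, for each outcome. On its content: "The primary RM ANCOVA model will include time, treatment arm, and the stratification factors". The covariance is unstructured, and Toeplitz, autoregressive and compound-symmetry structures are compared in secondary models. No separate analysis is given for FEV1.

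The operational sections give a different schedule. Section 7.1 has "spirometry (FEV1) at baseline and Week 12". Of self-reported dyspnea and spirometry it says: "These measures will be administered in-person at the NCORP site during baseline and post-intervention (Week 12) assessments". The Week 6 assessment is a shorter set of questionnaires, by mail and/or telephone.

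Section 12.5 handles another measure collected only at baseline and 12 weeks, salivary cortisol, by analysis of covariance: the 12-week value is the dependent variable, and its baseline level and treatment group are covariates.

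**The concern.** The statistical section describes a Week 6 FEV1 value that nobody is scheduled to collect. Read literally, FEV1 would show a whole missing visit, and it would enter a repeated-measures model with only one post-baseline value.

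Respiratory functioning is a named secondary outcome (objective 1.2), and FEV1 is its only objective measure. Section 12.4 also says that the variability estimates from this model will inform the size of the next trial. For FEV1, both the treatment estimate and the variability estimate depend on what is done with the baseline value. The plan collects that value but does not place it in the model.

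**Working it through.** **Occasions.** The plan's own figure is three occasions for pulmonary function (12.1 and 12.4). The count from the other sections is:

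| Place | FEV1 occasions |
|---|---|
| 12.1, 12.4 | baseline, Week 6, Week 12 (3) |
| Schema, Section 3, 7.1 | baseline, Week 12 (2) |
| 7.2 baseline list and 7.4 Week 12 list | one in each (2) |
| 7.3 Week 6 list | none; questionnaires, activities form and weekly call form only |
| 7.8 table | two marks for spirometry, against three each for the Cancer Dyspnea Scale and Cancer Worry Scale |

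The figure of three is not reproduced. FEV1 has two occasions, and 2 − 1 = 1 of them is post-baseline. Section 12.1 speaks of respiratory rather than pulmonary function. Dyspnea is listed beside it as a separate item, so the term points to spirometry.

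**What the 12.4 model becomes for FEV1.** With k response occasions, an unstructured covariance has k(k+1)/2 parameters.

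- Baseline as covariate: k = 2 for HADS, the Cancer Worry Scale and the Cancer Dyspnea Scale (3 parameters), but k = 1 for FEV1 (1 parameter). Time then has one level and coincides with the intercept. Intercept, time, two arm terms, one dyspnea-stratum term and baseline make 6 columns of rank 5. Choosing among covariance structures has no content. The arm effect remains estimable: without the redundant time term, this is ordinary ANCOVA at Week 12.
- Baseline as response: k = 3 for the questionnaires (6 parameters) and k = 2 for FEV1 (3 parameters). Intercept, time, two arm terms and one stratum term make 5 columns of rank 5, so the model can be fitted. With two occasions, Toeplitz, autoregressive and compound symmetry coincide, at 2 parameters each.

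**What depends on the role of baseline.** The documents do not state whether baseline is a covariate or a response.

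(a) *Week 12 as response, baseline FEV1 omitted.* Let r be the correlation of baseline with Week 12 FEV1 within arm and stratum. It is assumed here, because the documents give none. The residual variance is σ² without baseline and σ²(1 − r²) with it, so the ratio of standard errors is 1/√(1 − r²):

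- r = 0.80: 1/√0.36 = 1.67
- r = 0.90: 1/√0.19 = 2.29
- r = 0.95: 1/√0.0975 = 3.20

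The same ratio applies to the residual standard deviation that would be reported as the outcome's variability.

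(b) *Baseline as response, no time-by-arm term.* Let the arm differences be d₀ at baseline and d₁₂ at Week 12. Generalised least squares weights the two visits in proportion to V⁻¹1. With equal variances and correlation ρ, both entries equal 1/(σ²(1 + ρ)), so each weight is 1/2 for any ρ. The arm term estimates (d₀ + d₁₂)/2, which is d₁₂/2 when d₀ = 0.

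(c) *Is the missing Week 6 test the cause?* No. The ratio in (a) contains only r. For (b), take an outcome that does have three visits, with equal variances, exchangeable correlation and a constant post-baseline difference d. The same model would estimate (0 + d + d)/3 = 2d/3, so the dilution is there as well. Correcting the FEV1 timing alone would remove neither effect.

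**The case against.** The strongest reply is that 12.4 can be read more generously. The model is called an ANCOVA, and it is to give adjusted post-treatment estimates of variability, which suggests post-treatment values as the response and baseline as a covariate. The dose comparison is to be taken at 12 weeks from this same model, which suggests visit-specific arm estimates rather than one average over visits. The list of terms need not be exhaustive. On that reading, FEV1 gets an efficient Week 12 ANCOVA.

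This largely stands. It is a plausible intention, so a reader should not infer that every reading of the plan gives an inefficient or diluted estimate. It does not make the text complete. The term list contains neither baseline FEV1 nor a time-by-arm term, whereas 12.5 writes the baseline covariate out for cortisol.

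It is also fair that FEV1 carries no decision. The primary objective is feasibility, the go/no-go and dose-selection rules use anxiety alone, and the operational sections agree among themselves, so sites would not be misled about spirometry.

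Two other stronger inferences fail. One is that FEV1 cannot be analysed as planned; both forms of the model yield an arm estimate. The other is that the loss of precision or the halving comes from the absent Week 6 test; part (c) of the check shows that it does not.

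**Conclusion.** The contradiction in timing is certain and nothing in the documents resolves it: three occasions stated in Section 12, two scheduled everywhere else. The three-occasion repeated-measures analysis therefore does not match the FEV1 data, although FEV1 remains analysable.

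The second, separate point is that the role of baseline is unstated. If baseline FEV1 were omitted, the standard error would be 1.7 to 3.2 times the baseline-adjusted one. That range rests wholly on the assumed r of 0.80 to 0.95. If baseline were a response with no time-by-arm term, the estimate would be half the Week 12 difference, given equal variances and balanced baselines. These are conditional sizes, not predictions of what the analyst would do.

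The impact is limited to a secondary outcome and its variability estimate. HADS anxiety is scheduled at all three occasions, and neither the dose selection nor the sample size of 75 uses FEV1. The point merits correction because the correction is nearly free.

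**What to change.** - In 12.1 and 12.4, state that FEV1 is measured at baseline and Week 12 only.
- Analyse Week 12 FEV1 by ANCOVA with baseline FEV1, treatment arm and the same stratification factors as the primary model, in line with the use of baseline levels for cortisol in 12.5. The schema lists site and dyspnea as stratification factors, while 12.3 lists dyspnea only. Whichever set the primary model uses should carry over.
- Keep the repeated-measures model for the outcomes with a Week 6 value, and state there too whether baseline is a covariate or a response. If it is a response, include the time-by-arm term.
- Say how participants without a Week 12 FEV1 are handled. Section 7.10 expects about 20% attrition, or 0.20 × 75 = 15 participants. The multiple-imputation sensitivity analyses already in 12.4 can be named for FEV1.

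The cost is a few sentences in Section 12, with no added visit, test or participant.

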12.2 Sample Size/Accrual Rate

The sample size for this trial will be based on statistical selection theory criterion as described by Simon et al.⁷⁷ For a selection trial, one simply chooses the regimen that results in the "best" response. While Simon used this idea in the context of choosing the regimen with the best tumor response, the idea is applicable to outcomes with other distributions (in addition to the binomial). In our trial, the response is self-reported anxiety, which we will assume is normally distributed, so the best regimen will be the one with the lowest mean anxiety score. We will proceed to a phase III trial if one of the RESPeRATE intervention arms results in the least anxiety, and the mean anxiety score in that group is at least 0.5 standard deviations (SD) less than mean anxiety score in the control group. The sample size is chosen to ensure a high probability of selecting the best arm, assuming that the mean anxiety score in the low dose arm is 0.5 SD less than the mean in the control group and the mean anxiety score in the high dose arm is 1.0 SD less than the mean in the control arm. Under these assumptions, we used

simulations to determine the sample size needed in each group to ensure that the probability of selecting the best regimen was 90%. We randomly selected n independent observations from the normal distribution with an SD = 1, calculated the mean anxiety scores for each group, and selected the group with the least observed mean. This was repeated 200,000 times. The probability that the best regimen was chosen is calculated as the proportion of times (of the 200,000 repetitions) that the group with the true lowest mean was selected. In addition to selecting the best regimen, we will only pursue a subsequent phase III trial if there is some evidence of effect. Thus, we will require that the mean in the best regimen is at least 0.5 SD lower than the mean for the control group. Using simulations, we find that 20 patients per group provides 90% probability that the best regimen will be chosen and the mean in that group be at least 0.5 SD lower than the mean in the control arm. Assuming a 20% dropout, we will accrue a total of 75 participants to this study (20x3/.8). Assuming no effect of the RESPeRATE device, we have 90% probability of stopping with the phase II trial.

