Salivary Cortisol Analyses. Participants with endocrine disorders (e.g., diabetes and thyroid disorders) or on steroid-based medications are excluded from the cortisol portion of the study (topical hydrocortisone cream permitted). Cortisol levels will be assessed upon awakening, 30 minutes post-awakening, and at bedtime for three consecutive days at baseline and three consecutive days at 12 weeks. Several measures will be derived from the three daily cortisol values, including the mean levels at each time, the mean cortisol awakening response (CAR – change in cortisol from awakening to 30 minutes), the area under the curve (AUC), and the diurnal slope (change in cortisol between awakening and bedtime). Scatterplots and correlations will be used to quantitate the associations between these measures, and anxiety at each time (baseline and 12 weeks) as well as association between the change in cortisol measures and the change in anxiety. Additionally, mixed effects models, as described above, will be used to assess the association between baseline cortisol and changes in anxiety over time. To assess group differences in cortisol parameters, each of these measures at 12 weeks will be used as dependent variables in analysis of covariance models, using appropriate transformations as needed. Baseline levels of the measures will be used as covariates along with treatment group.

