12.8 Evaluation of Response

Tumor response is not an outcome. Response for this study will be the change in anxiety from baseline to 12 weeks, and this outcome will be assessed in all participants. Analysis of this outcome is described above in Section 12.4.

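### Dose selection is defined as lowest mean anxiety in 12.2 but as greatest improvement in 12.1, 12.4 and 12.8, and the primary model as listed gives no baseline-adjusted week-12 estimate for either

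*Combined protocol and SAP*

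**What the plan says.** Section 12.2 bases the sample size on a selection design, "so the best regimen will be the one with the lowest mean anxiety score". It gives no time point for that mean, and its simulation draws one score per patient with no baseline value. A phase III trial follows only if the selected arm is an active one and lies at least 0.5 SD below control.

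Section 12.1 states the rule differently: "The optimal dose will be defined as the one that results in the greatest improvement in anxiety scores at 12 weeks". Section 12.4 repeats this and takes the estimate from the repeated-measures ANCOVA. Section 12.8 adds: "Response for this study will be the change in anxiety from baseline to 12 weeks".

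On the model, 12.4 says: "The primary RM ANCOVA model will include time, treatment arm, and the stratification factors". The stratification factor in 6.4.2 and 12.3 is the dyspnea score, split at 8; the schema also lists site. The later models give age, sex and stage as example covariates. Baseline HADS-A is named in neither place, and no time-by-arm term is listed. For cortisol, by contrast, 12.5 is explicit: "Baseline levels of the measures will be used as covariates along with treatment group". The methylation and expression models in 12.5 also name their baseline values.

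**The concern.** Choosing the dose for the next trial is Objective 1.3, and 12.4 says the chosen dose will be carried forward. A week-12 level and a change from baseline are sure to rank the arms in the same order only if mean baseline HADS-A is equal across arms or the estimate is adjusted for it.

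The design does little to secure that equality. Randomization is stratified on dyspnea, and section 2.1a puts the anxiety-dyspnea correlation at only 0.3. Section 4.1.4 admits patients on the Distress Thermometer or the worry screener alone, so baseline HADS-A is not confined to 8 or more.

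At 20 to 25 patients per arm, two analysts following different sections could therefore carry forward different doses from the same data, and the choice between the rules could be made after the data are seen.

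**Working it through.** **Inputs from 12.2.** SD 1; true means 0 (control), -0.5 (low dose) and -1.0 (high dose); 20 evaluable per arm; margin 0.5 SD; 20% dropout. **Assumed, because the documents give no value:** baseline-to-week-12 correlation r = 0.3, 0.5 or 0.7; equal SD at both times; bivariate normality; adjustment slope treated as known. Selection by the entry cut-offs is not modelled.

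**Variance of an arm mean, v**
- raw week-12 mean: 1/n
- raw change: 2(1 - r)/n
- baseline-adjusted mean: (1 - r²)/n

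**Selection probability.** The high dose is chosen with the margin if low minus high exceeds 0 and control minus high is at least 0.5. Both differences exceed their limits by 0.5 on average, have SD √(2v), and correlate 0.5. The probability is therefore Φ₂(z, z; 0.5) with z = 0.5/√(2v). With no true effect, stopping requires both active arms to be less than 0.5 below control, which gives the same expression. So one number serves as both the correct-selection and the stop probability.

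**The plan's figures.** Raw mean, n = 20: v = 0.05, √(2v) = 0.316, z = 1.581, Φ₂ = 0.90. Simulation gives 0.900 for correct selection and 0.901 for stopping. Total: 60/0.8 = 75. All four stated figures reproduce.

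**The three rules at n = 20**

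| r | raw mean | raw change | baseline-adjusted |
|---|---|---|---|
| 0.3 | 0.90 | 0.85 | 0.91 |
| 0.5 | 0.90 | 0.90 | 0.94 |
| 0.7 | 0.90 | 0.96 | 0.975 |

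The false-go probability is one minus each entry. It is 0.10 for the raw mean and about 0.09/0.06/0.025 after adjustment.

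**How often raw mean and raw change disagree on low versus high dose.** The two between-arm differences correlate c = √((1 - r)/2).
- Equally effective doses: arccos(c)/π = 0.298, 0.333, 0.373 at r = 0.3, 0.5, 0.7, that is 30-37%.
- Doses 0.25 SD apart: 0.226, 0.236, 0.240, about 23-24%.
- The plan's gap of 0.5 SD: 0.099, 0.085, 0.067, about 7-10%.

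**Baseline imbalance.** At 25 per arm, the chance that the two active arms differ by more than 0.25 SD in mean baseline is 2(1 - Φ(0.25/√(2/25))) = 2(1 - Φ(0.884)) = 0.38.

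**What the listed model yields**
- Baseline as one of the repeated outcomes: main effects of time and arm make the fitted profiles parallel, so the fitted change is the same in every arm.
- Weeks 6 and 12 as outcomes, no baseline covariate: the arm effect is a level pooled over both weeks.
- Weeks 6 and 12 as outcomes, baseline covariate assumed: the effect is adjusted but still pooled over both weeks.

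None of these is an arm-specific, baseline-adjusted estimate at week 12.

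**The case against.** The best reply is that baseline adjustment was intended. The model is called ANCOVA although every listed term is categorical. Section 12.4 refers to adjusted post-treatment estimates, and 7.2 makes the screening HADS the baseline value. A list of what a model will include need not be exhaustive, and age, sex and stage are only examples. This stands as far as it goes: underspecification is at least as likely as a deliberately unadjusted analysis. It does not supply the missing terms, and 12.5 shows that the plan names baseline covariates elsewhere.

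It can also be said that 12.2 is only a sample-size rationale and that improvement is the operative rule. That is a fair reading, and randomization makes both rules favour the same dose in expectation. The 90% figures then still belong to a statistic other than the one to be used.

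A reader might infer that the stated 90% is wrong, since raw change gives 0.85 at r = 0.3. The documents do not support this. No passage explicitly specifies selection on raw change, and the same rule gives 0.90 at r = 0.5 and 0.96 at r = 0.7. Nor does the 30-37% disagreement measure harm: it arises when the doses are equal and neither choice is wrong.

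**Conclusion.** The plan words its selection statistic in two ways, and the model meant to supply the estimate is incompletely specified. The practical size is modest under the plan's own effects (about 7-10% disagreement) and larger if the doses are closer (about 23-24% at 0.25 SD). These figures compare raw mean with raw change at 20 per arm and rest on the assumed r of 0.3 to 0.7.

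This is not a sample-size error. A reader might also conclude that the sections are bound to select different doses; they are not, since divergence needs a chance baseline imbalance. The correction is worth making because it removes an ambiguity about Objective 1.3 and improves the selection at no cost in patients.

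**What to change.** Use one selection statistic in 12.1, 12.2, 12.4 and 12.8: the week-12 least-squares mean HADS-A from a model with weeks 6 and 12 as outcomes and baseline HADS-A, time, arm, time-by-arm and the stratification factors as terms. Both additions are needed. Baseline HADS-A makes level and improvement equivalent, because adjusted mean and adjusted change then differ by the same constant in every arm. The time-by-arm term makes the estimate specific to week 12.

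Apply the same adjusted means to the 0.5 SD comparison with control, state that the SD is the unadjusted HADS-A SD, and repeat that threshold beside the selection sentence in 12.4.

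The cost is a wording change and two model terms. Baseline HADS-A is already collected, and the total of 75 does not need to rise.
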